### **Month 9 [Day 270 ± 14 days]: Telephone Contact**

The following will be performed:

- Adverse events.
- Concomitant medications.
- Drug compliance and agent diary review.

The telephone call can be replaced with alternate forms of communication preferred by the participant – text, email, health portal message or other where local policy allows, as long as all required information is collected.

### **Month 12 [Day 365 ± 30 days]: Telephone Contact**

The following will be performed:

- Adverse events.
- Concomitant medication.
- Premenopausal women should be reminded that they are strongly advised not to become pregnant while on study and should continue using appropriate contraceptive methods.
- Mail or email the 4-OHT Diary to the participant. Ask the participant to record their daily use of agent on the 4-OHT Diary; using a new Diary for each Canister.
- Participants will be asked to extend their gel application and will be reconsented following the CIRB remote consent procedure for the extended gel application.
- Ship or have the participant pickup a new 6-month supply of the study agent.
- Instruct the participant to keep all used canisters and to bring the canisters with all of their completed Diaries to the next in person clinic visit.
- Drug compliance and agent diary review.

- Mail or email the **BESS QUESTIONNAIRE** to the participant ahead of the telephone visit, if possible. Ask the participant to fill it out ahead of the visit, to sign and date the form at the time of completion, and keep it. Collect the information during the visit, if allowed by the institution and if the participant feels comfortable to discuss the responses over the phone. Participants should return the **BESS QUESTIONNAIRE** at their next in person visit. If you were not able to mail/email the **BESS QUESTIONNAIRE** ahead of the telephone visit, collect the information over the phone, if possible. Record the answers.
- Participants will be reminded of the need to reschedule their mammogram within the next 6 months.
- Participants that do not want to extend their gel application should be taken off agent and asked to allow the collection of their next available mammogram for study purposes.

## 7.4 Evaluation at Completion of Study Intervention

### Month 13-18

The following will be performed:

- Physical exam, including a breast examination.
- Vital signs, weight.
- Laboratory tests will include the following:
  - CBC (hemoglobin, hematocrit, RBC, WBC, platelet count)
  - Total bilirubin
  - AST (SGOT)/ALT (SGPT)
- In women who were considered premenopausal at baseline: FSH, LH, estradiol.
- A urine or serum pregnancy test will be performed. The urine pregnancy test must be done in the clinic. If the pregnancy test result is positive at the 13-18 Month visit, follow the pregnancy to term and complete the Outcome of Pregnancy CRF. Do not take the participant off study until the completion of the pregnancy when the outcome of pregnancy is known.
- Bilateral mammogram. The raw images must be obtained (see instructions in Section 8.1) for study purposes.
- For participants who underwent the baseline breast biopsy, the biopsy will be repeated if participant extended their gel application.
- Blood draw for research biomarkers
- Adverse events.
- Concomitant medication.
- Collect unused study agent.
- Compliance check will be performed by evaluating the participant's agent diary.
- BESS Questionnaire (refer to Appendix E).
- Tobacco and Alcohol use assessment will be performed at Month 12, using the Month 12 questionnaires (see Appendix G "Alcohol and Tobacco Use Assessment Questionnaires – Month 12").
- Participants will be reminded of the need to return for their next annual mammogram (Month 24 + 8 Months), which is their standard clinical high risk follow-up visit.

## 7.5 Post-intervention Follow-up Period

### Month 24 + 8 Months

- Collection of the standard of care bilateral mammogram images. Raw images must be obtained for study purposes (see instructions in Section 8.1).

## 7.6 Methods for Clinical Procedures

### Breast core biopsy (see also Section 10.2):

The breast core biopsy (image guided) is optional. A 14-gauge needle will be used. Every effort will be made to collect 4 cores of tissue, with the minimum of 2 cores per participant.

Tissue will be considered adequate for research assays if the H&E stained slide from the block demonstrates at least one TDLU in every tissue core. One H&E slide will be prepared for adequacy and histological assessment. Usually each terminal duct lobular unit contains 200 to 2500 cells. If no terminal duct lobular units are seen, deeper sections will be obtained. Subsequent slides will be used for biomarker analysis. Refer to Section 10.2 for tissue collection and handling procedures.

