#### Tissue Biomarkers

Overview: Tissue biomarkers have been selected to interrogate the following targets that represent:

- a) Structure-function activity of terminal ductal lobular units (TLDUs) by counting acinar density
- b) Breast tissue density by assessing the patterns of collagen matrix
- c) Hormone-mediated cellular activity by measuring the transcriptional expression levels of ER-alpha and ER-associated genes (SETER/PR index)

- d) Pharmacogenomic response to endocrine therapy by measuring Ki67 protein by immunohistochemistry and aurora kinase-alpha gene expression
- e) Inflammatory response to 4-OHT therapy by measuring COX2 and p16 proteins, and recruitment of CD68 monocytes.

All biomarkers will be compared in biopsies obtained before and after exposure to the 4-OHT gel, in order to explore pharmacodynamic responses of interest. That said, the baseline measures will also be evaluated, particularly for items a-c (above) that might be less likely to change in response to short-term exposure, but combine to provide the cellular, matrix and targeted molecular context of the tissues in each participant prior to exposure to treatment.

*a) TDLU Involution:* TDLU involution is characterized by a reduction in the number and size of TDLUs and their secretory acinar units. Reduced involution in TDLUs has been associated with increased risk of breast cancer in several studies of women with benign breast disease. Furthermore, a recent study showed that, especially amongst premenopausal women, reduced TDLU involution was associated with higher area and volumetric MD; indicating that TDLU involution and MD are correlated markers of breast cancer risk. In continuation of this, there is also data suggesting that increased MD and reduced TDLU involution are actually independent risk factors for breast cancer. Taken all these together, in our proposal, as an exploratory endpoint, our aim is to assess TDLU involution, correlate with MD and evaluate whether baseline TDLU involution correlates/predicts change in MD induced by 4-OHT gel. The TDLU density (acini per TDLU) is readily determined from pathologic review of the same routine H&E stained tissue sections that are usually used for diagnosis using image analysis tools for area-based quantitation.

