c) *SETER/PR index*: We have previously published a gene expression index for estrogen receptor-related gene expression that was theragnostic for prognosis following endocrine therapy for early (node-negative), and following chemo-endocrine therapy for higher-risk (node-positive) hormone receptor-positive and HER2-negative HR+/HER2- breast cancers. However, it is only recently that we have been able to measure the SET index from formalin-fixed and paraffin-embedded tumor tissues from residual disease. This SETER/PR index measures 18 transcripts that are strongly correlated with both ER and PR expression, and are not related to proliferation. The SETER/PR index compares the expression of those 18 transcripts to 10 reference transcripts within the assay, and also includes probes to measure the expression levels of *ESR1*, *PGR*, *ERBB2*, and *AURKA* (aurora kinase A) transcripts. The reproducibility of the SETER/PR index exceeds 99% across batches and technicians, and the assay is performed on a single 10µm tissue section from FFPE blocks of biopsies from breast cancers. We expect that the less cellular samples from benign breast tissues would require at least 10 TDLUs (usually obtained from 3 x 10µm sections from core biopsies). Furthermore, the SETER/PR index is independently prognostic following endocrine therapy in metastatic breast cancer samples, and in primary tumor samples from node-positive or node-negative breast cancers. In an exploratory in silico analysis, we observed no change in SET index values measured from sequential core biopsies of invasive HR+/HER2- cancers taken before and after a 2-week exposure to neoadjuvant endocrine therapy. That result was different from the pharmacodynamic reduction in the proliferation-related signature of genomic grade index that was reported in the same samples. However, the observed stability of the SET index during short-term endocrine therapy might be consistent with a long-term treatment that continues to have efficacy over a long time. Otherwise, rapid suppression would probably render the treatment ineffective over the longer term. We do not know whether this will also be the case with non-malignant tissues – perhaps shorter-term suppression of endocrine capacity may be possible.

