### **8.3 Exploratory Endpoints**

8.3.1 To compare the Cumulus vs. Volpara vs. LIBRA breast density measurement methods to estimate percent change in mammographic breast density from baseline to Month 12 in women applying 2mg of 4-OHT gel per breast vs. placebo.

8.3.2 To perform correlation of drug concentrations in the plasma and the tissue.

8.3.3 To evaluate plasma measurements of Insulin-like growth factor (IGF) pathway members, C-reactive protein (CRP), and estradiol.

8.3.4 To compare the 2D natural vs. 2D synthetic breast density measurement using the Cumulus method to estimate percent change in mammographic breast density from baseline to Month 12 in women applying 2mg of 4-OHT gel per breast vs. placebo.

8.3.5 To evaluate tissue biomarkers (among women undergoing optional pre- and post-treatment biopsies):

- Structure-function activity of TLDUs will be evaluated by counting acinar density.
- Breast tissue density will be evaluated by assessing the patterns of collagen matrix.
- Hormone-mediated cellular activity will be evaluated by measuring the transcriptional expression levels of ER-alpha and ER-associated genes (SETER/PR index).
- Pharmacogenomic response to 4-OHT will be evaluated by measuring Ki67 protein by immunohistochemistry and aurora kinase-alpha gene expression.
- Inflammatory response to 4-OHT therapy will be evaluated by measuring COX2 and p16 proteins, and recruitment of CD68 monocytes by immunohistochemistry.

8.3.6 To examine whether any reductions in mammographic density seen after 1 year of 4-OHT vs. placebo gel application persist at 24 months (or longer under the COVID-19 Contingency Plan), one year after gel application has stopped.

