**Submission of mammographic data**

Digital mammography systems produce images in two forms, commonly referred to as the ‘raw’ image and the ‘processed’ images. For analysis of mammographic density **raw images** will be required, both raw images and ‘processed’ images will be collected.

All centers involved perform Digital Breast Tomography. As the current standard for 3D digital breast tomography is to include 3D images and either a conventional dose 2D mammogram or a synthesized 2D image, both the 3D and 2D images should be submitted. Only the 3D images will be analyzed, but 2D images will also be collected to create a data resource for future studies.

Digital files must be in DICOM format. Ensure that software used to de-identify images does not remove the date of the scan and specifics of the physics/image acquisition such as breast thickness and compression.

These files may be submitted electronically preferably with TRIAD. Alternatively, the images and reports may be submitted via secure portal to UT MD Anderson.

Research Blood collection:

Peripheral blood will be obtained by venipuncture at baseline, at 6 and at 12 months.

For the purpose of tracking samples: a pre-printed label will be attached to identify all sample vials.

Approx. 25 mL of blood will be collected and processed as per the Laboratory Manual. Refer to the Laboratory Manual for storage instructions.

Breast Core Biopsy (see also section 7.6):

The breast core biopsy (image guided) is optional. A 14-gauge needle will be used. Every effort will be made to collect 4 cores of tissue, with the minimum of 2 cores per participant at each time point.

Tissue will be considered adequate for research assays if the H&E stained slide from the block demonstrates at least one TDLU in every tissue core. One H&E slide will be prepared for adequacy and histological assessment. Usually each TDLU contains 200 to 2500 cells. If no TDLUs are seen, deeper sections will be obtained. Subsequent slides will be used for biomarker analysis.

- Samples should be collected and processed in the order below:

Breast Biopsy Sample Priority:	
Sample 1	FF
Sample 2-3	PE
Sample 4	RNALater®

- **Flash Frozen (FF) sample:** Biopsy sample (#1) should be placed directly into pre-labeled cryovial and snap frozen on isopentane, or liquid nitrogen, and then temporary storage on dry ice for transport to freezer at -80°C for storage.

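### One adequacy rule for all tissue assays, a TDLU in every core, makes evaluability for TDLU involution depend on the outcome and can withhold measurable tissue

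*Combined protocol and SAP*

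**What the plan says.** The protocol states the adequacy rule twice, in Section 7.6 and in the biopsy part of Section 10.2, each time for research assays as a whole: tissue counts as "adequate for research assays if the H&E stained slide from the block demonstrates at least one TDLU in every tissue core". Both places add a second step: "If no terminal duct lobular units are seen, deeper sections will be obtained" (Section 7.6) and "If no TDLUs are seen, deeper sections will be obtained" (Section 10.2).

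Section 2.3, Tissue Biomarkers, item a, gives the biology: "TDLU involution is characterized by a reduction in the number and size of TDLUs and their secretory acinar units". The measure it names is narrower: "The TDLU density (acini per TDLU) is readily determined from pathologic review". Section 8.3.5 words the endpoint similarly: "Structure-function activity of TLDUs will be evaluated by counting acinar density".

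Tissue allocation is in Section 10.2. With four cores, the first is flash frozen, the second and third go to paraffin, and the fourth goes into RNA stabiliser. With the minimum of two cores, one is frozen and one goes to paraffin. An H&E slide from the block can therefore show only one or two cores.

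Section 2.3 also plans collagen pattern (item b) and the fatty/non-fatty ratio (item c). For the SET index it expects that benign tissue "would require at least 10 TDLUs", usually obtained from three 10 µm sections.

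No section says what happens to tissue that stays inadequate, or asks for adequacy by arm or visit. The multiple imputation in Section 13.6 supplements the primary analysis and does not address this.

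**The concern.** An adequacy check should separate usable from unusable tissue without reference to the result. Here the check is the presence of the structure whose loss is the outcome. Tissue without TDLUs cannot pass, whether the needle missed glandular tissue or the lobules have regressed, and the plan does not separate the two.

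This matters at both visits. At baseline, Section 2.3 plans to relate involution to mammographic density and to ask whether it predicts density change. Losing the most involuted tissue narrows the range of that predictor, in a trial that enrols women up to age 69. After treatment, if 4-OHT causes involution, more active-arm than placebo biopsies would fail, and pre/post pairs would be missing in a way related to response.

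Two further losses have nothing to do with limits of measurement. A biopsy with TDLUs in one paraffin core and none in the other fails, although acini per TDLU can be counted. Collagen pattern and fatty/non-fatty ratio fall under the same gate although neither needs a TDLU. Section 2.3 presents these tissue markers as candidate surrogates, and a marker shrunk toward no effect could be set aside wrongly.

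**Working it through.** The plan gives no figure to reproduce: TDLUs per core, biopsy uptake and the inadequacy rate are all absent. What follows illustrates mechanism and direction only.

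**Inputs.** From the documents: a TDLU is required in every core, and there are two paraffin cores when four are taken (Section 10.2). Assumed: TDLU counts per core are independent Poisson with mean m, with m from 0.5 to 5, and no biopsy is rescued by deeper sections.

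**Formulas, two paraffin cores**
- Passes (TDLU in both cores): (1 − e^−m)²
- Mixed (TDLU in one core only): 2·e^−m·(1 − e^−m)
- No TDLU in either core: e^−2m

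**Worked case, m = 1.5.** e^−1.5 = 0.223. Passes: 0.777² = 0.604. Mixed: 2 × 0.223 × 0.777 = 0.347. None: 0.223² = 0.050. About 40% fail; about 35 of those points are mixed biopsies and 5 have no TDLU.

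| Mean TDLUs per core | Passes every-core rule | Mixed | None |
|---|---|---|---|
| 5 | 98.7% | 1.3% | 0.0% |
| 2.5 | 84.3% | 15.1% | 0.7% |
| 3 | 90.3% | 9.5% | 0.2% |
| 1.5 | 60.4% | 34.7% | 5.0% |
| 2 | 74.8% | 23.4% | 1.8% |
| 1 | 40.0% | 46.5% | 13.5% |
| 0.5 | 15.5% | 47.7% | 36.8% |

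**Difference created by a true halving.** Going from 3 to 1.5 per core, the every-core rule passes 90.3% against 60.4%, a gap of 29.9 points. Requiring a TDLU in any core passes 1 − e^−2m: 99.8% against 95.0%, a gap of 4.8 points. From 5 to 2.5 the gaps are 14.4 and 0.7 points. From 2 to 1 they are 34.8 and 11.7 points.

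**Single paraffin core.** Mixed biopsies cannot occur, and the rule fails e^−m: 5.0% at m = 3 and 22.3% at m = 1.5. Every core and any core are then the same rule.

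**Effect on a mean TDLU count.** Among passing cores the mean is m/(1 − e^−m). A true 50% fall then appears as 20%, 32%, 39% and 46% for starting means of 1, 2, 3 and 5. A 25% fall from a mean of 5 appears as 24%. These figures show direction only, because the plan specifies no analysis of TDLU count. For acini per TDLU, the same direction needs a further assumption: that breasts with fewer TDLUs also tend to have smaller ones, in line with the definition in Section 2.3.

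**The case against.** A reader might infer that women with the most complete involution are removed, so that responders disappear from the active arm. The documents do not support that, for these reasons.

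- **Exclusion is not written.** It is inferred from the phrase about adequacy for research assays. The H&E slide is also meant for histological assessment, and Section 13.5 uses all available data. This stands, although the rule has little purpose unless it gates something.
- **The measure is acini per TDLU or acinar density, not a TDLU count.** With no TDLU, acini per TDLU is undefined under any adequacy rule, and partial involution in surviving TDLUs is still captured. This stands for biopsies with no TDLU. It does not cover mixed biopsies.
- **Deeper sections rescue some biopsies,** so the failure rates above are upper illustrations. This stands. However, the stated trigger is that no TDLU is seen, while the rule requires one in every core, so a mixed biopsy may not trigger rescue. Where deeper cutting happens, its extent depends on the outcome.
- **The size rests on assumption.** Section 2.3 says items a to c may be less likely to change with short exposure, although item c does name lower TDLU density as a possible response. If the 10-TDLU remark implies about 5 per core, itself an assumption, the mildest rows apply.
- **SET.** A reader might infer that the rule admits tissue the protocol itself regards as too sparse. The two figures have different bases: a floor on one H&E slide against an expectation usually met from three sections. The rule does not secure 10 TDLUs, but it does not show a shortfall either.
- **Scoring absence as maximal involution** could turn a sampling miss from one or two cores into a response. This stands, and it is why the fix uses that score only in a sensitivity analysis.

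**Conclusion.** The point holds in a limited form. The shared rule makes evaluability for the exploratory TDLU objective depend on the outcome at both visits. Read as a gate, it discards measurable mixed biopsies and withholds two assays that need no TDLU. The plan has no rule for valid tissue in which TDLUs remain absent. The direction is toward no effect if 4-OHT causes involution.

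The size cannot be determined from the documents. In the two-core illustration, a true halving produces adequacy gaps from about 14 points (5 to 2.5 per core) to about 35 points (2 to 1), before any rescue by deeper sections. These gaps rest on assumed Poisson counts and an assumed effect, so they do not show that responders are lost. The endpoint is exploratory and confined to the optional biopsy subset; the primary conclusion is unaffected. This is a cheap improvement, not a flaw in the trial's main comparison.

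**What to change.** Make adequacy assay-specific in Sections 7.6 and 10.2, and state that the rule refers to the one or two paraffin cores.

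- **(a) Collagen pattern and fatty/non-fatty ratio:** require only evaluable breast tissue.
- **(b) Acini per TDLU:** use every biopsy with at least one TDLU in any core.
- **(c) TDLU absence:** record valid breast tissue without TDLUs as its own category, separate from sampling failure. Report adequacy and TDLU absence by arm and visit. Add a sensitivity analysis that treats absence as complete involution, using counts from the first section only.
- **(d) Epithelial assays such as Ki-67:** keep the TDLU requirement with deeper sections.
- **(e) SET:** report the TDLU count of the assayed sections against the expected 10. Do not impose a new hard cutoff, which would select on TDLU number again.

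The cost is wording in two sections and slightly more pathology recording, on the same slides and with no added procedure. The downside is that some results will come from sparser tissue.

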## 8. CRITERIA FOR EVALUATION AND ENDPOINT DEFINITION

### 8.1 Primary Endpoint

The primary objective of this study is to evaluate mammographic density (MD) changes induced by 4-OHT gel versus placebo in women with mammographically dense breast. Our hypothesis is that 4-OHT will reduce MD. Baseline and 12 months mammogram [or mammograms from Month 13-18 under the COVID-19 contingency plan] will be evaluated for 4-OHT effect using Cumulus software for the primary endpoint evaluation. Analysis will be based on tomosynthesis imaging using the 2D synthetic image.

MD will be classified using BIRADS descriptions on mammographic reports (i.e: predominantly adipose tissue, scattered fibroglandular densities, heterogeneously dense or extremely dense). BIRADS MD assessment is a consistently utilized measure of breast fibroglandular tissue volume, which can be universally followed and reproduced. BIRADS is a scheme for putting the findings from mammogram screening into a small number of well-defined categories. In addition to BIRADS, baseline and follow up MD will be quantified and recorded using semi-automated software, Cumulus, which has been utilized in earlier density assessment studies. Cumulus reading will be centralized with the reader blinded to the timepoint and treatment group.

For the primary endpoint, the densest breast will be used.

At each institution mammographic images will be collected by a study specific data coordinator who will be overseen by the site Investigator. This data coordinator will also ensure that images are collected in usable format with appropriate de-identification. Follow the instructions in Section 10.2 for Collection and Handling of images.

In summary, the effect of utilized software on the density percent assessment is estimated to be minimal. Based on this, we will use:

- a) Downgrading of the baseline reported BIRADS breast density.
- b) Decrease in breast fibroglandular density by 10% or more as assessed by semi- and automated Breast Density software.

